1.3 Number of Patients

It has been determined that approximately 150 patients are appropriate to characterize the frequency of tumour genetic and proteomic markers at disease progression regardless of their prevalence. [Table 2](#) displays the precision of the estimated frequency of mutation when, for example, 50 evaluable paired biopsies are available.

The final analysis will be performed at study end, and when approximately 50 patients have evaluable paired biopsies upon progression. Assuming a 70% of rate of patients having a biopsy at both baseline and progression, and with an assumed technical failure rate of 30% of the samples (assume an overall failure rate of 51%), then we should expect approximately 50 evaluable paired biopsies to be available when approximately 103 of the 150 patients have progressed, which would be expected to occur approximately 38 months after the first patient is enrolled. This calculation assumes patients are recruited over 12 months, exponentially distributed progression times with a 19-month median and a 2-piece recruitment function that assumes an exponentially distributed recruitment rate.

Table 2 Precision of Estimates of Marker Frequency with 50 Available and Evaluable Paired Biopsies

Marker Frequency	95% confidence interval ^a
10%	(3%, 22%)
30%	(18%, 45%)
50%	(36%, 64%)

^a Exact binomial confidence intervals.

2. ANALYSIS SETS

2.1 Definition of Analysis Sets

The primary analysis set (PAS) will be used for the analysis of the primary endpoint. The full analysis set (FAS) will be used for all other efficacy and safety analyses.

2.1.1 Primary analysis set

The PAS will include all patients with evaluable paired biopsies, which are defined as follows: the first biopsy taken prior to osimertinib treatment and the second biopsy taken at any time between Investigator-assessed, RECIST 1.1-defined progression and before the start of any new anticancer treatment. If the Investigator judges the patient to have progressed but the

programmatically defined RECIST progression does not occur, the patient will still be considered evaluable. This analysis set will be used for the analysis of the primary endpoint.

2.1.2 Full analysis set

The (FAS) will include all patients who receive at least one dose of osimertinib. The FAS will be used for all efficacy and safety analyses.

[Table 3](#) summarises the population analysis sets for each outcome variable.

Table 3 Summary of outcome variables and analysis populations

Outcome variable	Population
Primary objective	
Proportion of patients with a given marker at progression as defined by the investigator	PAS
Efficacy data	
PFS, ORR, DoR, DCR, TTD, TFST	FAS
Subgroup analysis	
PFS, ORR, Best change in TL tumour size, TTD	FAS
Important patient and disease characteristics	FAS, PAS
Demography data	
Important patient and disease characteristics	FAS, PAS
Safety data	
Exposure	FAS
AEs	FAS
Laboratory measurements	FAS
Vital signs	FAS
Physical examinations	FAS
Electrocardiograms (ECGs)	FAS

Abbreviations: AEs = Adverse events; DCR = Disease control rate; DoR = Duration of response; ECG = Electrocardiogram; FAS = Full analysis set; ORR = Objective response rate; PAS = Primary analysis set; PFS = Progression free survival; TFST = Time to first subsequent therapy or death; TL = Target lesion; TTD = Time to treatment discontinuation or death.

2.2 Protocol deviations

The following general categories will be considered important protocol deviations which will be listed and discussed in the clinical study report (CSR) as appropriate for the study:

- Informed consent procedure deviation (eg, no informed consent signed prior to any screening procedure)
- Eligibility criteria deviation (eg, any inclusion criteria not met or exclusion criteria met)
- Received prohibited concomitant medications (or unable to stop use prior to receiving the first dose of study drug) or herbal supplements known to be potent inducers of cytochrome P450 (CYP) 3A4 (at least 3 weeks prior). Please refer to protocol Section 3.5 for those medications that are detailed as ‘not to be administered’ or being ‘restricted concomitant medications’. These will be used as a guiding principle for the physician review of all medications prior to database lock.
- Management of adverse events: Lack of prompt reporting of cases meeting Hy’s law criteria and serious adverse events (SAE) not being reported within 24 hours of awareness of the event.
- Tumour biopsy sample taken from lesion selected for RECIST assessment (unless only one lesion exists and the RECIST scans are performed within 14 days of screening biopsy).
- No baseline RECIST 1.1 assessment before start of treatment.
- RECIST 1.1 assessments not done every 8 weeks (± 7 days) in relationship to the date of first dose until RECIST 1.1 defined progression.
- Screening assessment not performed within 42 days prior to study drug initiation.

If the number of deviations which are considered to have the potential to impact the primary analysis is considered important, sensitivity analyses may be performed on subgroups. This will be decided during the data review meeting and before the database lock. The final classification of protocol deviations will be made prior to database lock. Any other deviations from monitoring notes or reports will be reported in an appendix to the CSR.

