3.1 Inclusion Criteria

For inclusion in the study patients should fulfil the following criteria:

1. Provision of informed consent prior to any study specific procedures (signed and dated Informed Consent Form).
2. Patients aged 18 years or older (specific age may vary according to country regulations for legal age).

3. Patients with histological confirmation of locally advanced or metastatic, non-squamous NSCLC who are not candidates for local curative treatment.
4. Patients with M1 stage according to the Tumour, Node, and Metastasis Classification of Malignant Tumours (TNM) version 7 including M1a (malignant effusion) or M1b (distant metastasis), or locally advanced disease that is not a candidate for curative treatment (including patients who progress after chemo-radiotherapy in stage III disease).
5. Patients with an EGFR deletion or mutation known (from tumour biopsy or plasma) to be associated with EGFR TKI sensitivity before treatment assessed by a local laboratory certified by Clinical Laboratory Improvement Amendments (USA sites) or an accredited local laboratory (sites outside of the USA).
6. Existence of measurable or evaluable disease (as per RECIST 1.1 criteria).
7. Possibility of obtaining sufficient tissue sample, via a biopsy or surgical resection of the primary tumour or metastatic tumour tissue, within the 60 days prior to study entry and at or after RECIST 1.1-defined progression. An archival biopsy is acceptable as long as there has been no intervening anticancer treatment since the time the biopsy was obtained to enrolment in this clinical study and as long as it was within 60 days of study entry. A sufficient tissue sample would consist of formalin-fixed, paraffin-embedded tumour tissue blocks, or at least 15 re-cut unstained sections from formalin-fixed paraffin-embedded tumour tissue block, presented on slides. Each section should be 5 μm thick.
8. WHO performance status 0-1.
9. Life expectancy \geq 12 weeks.
10. Capacity to swallow.
11. Patients able to complete study and within geographical proximity allowing for adequate follow-up.
12. Resolution of all acute toxic effects of previous anticancer therapy (which can only be adjuvant or neoadjuvant) or surgical interventions to Grade 1 according to the National Cancer Institute (NCI) CTCAE version 4.0 (except for alopecia or other side effects that the Investigator does not consider to be a risk to patient safety).

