5.1 Efficacy Assessments

5.1.1 Tumour evaluation

Following the screening assessment, subsequent tumour assessments will be conducted every 8 weeks (\pm 7 days) from study enrolment until 3.5 years (Day 1277), and then every 10 weeks (\pm 14 days) until RECIST 1.1-defined progression, even if a patient discontinues treatment prior to progression or receives other anticancer treatment. Tumour assessment will be performed using computed tomography (CT) or magnetic resonance imaging (MRI) of the chest, abdomen (including liver and adrenal glands) and pelvis. Any other sites where disease is suspected or known at screening must also be imaged. Scans will continue to be submitted up to the point of progression as assessed by the Investigator.

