5.3 Other Assessments

5.3.1 Resistance profiling

The samples will be collected and stored in a central laboratory/repository. Further details on sample processing, handling, and shipment are provided in the Laboratory Manual.

Mandatory tissue collection

The first mandatory tumour tissue biopsy will be collected at screening for baseline resistance profiling. Tumour tissue may be an archival or fresh tissue sample. An archival tissue sample is acceptable as long as there has been no intervening anticancer treatment since the biopsy was acquired and enrolment into this study, and as long as it is within 60 days of study entry.

The Investigator will be asked to provide formalin-fixed, paraffin-embedded tumour tissue blocks, or a at least 15 re-cut unstained sections from formalin-fixed paraffin-embedded tumour tissue block, presented on slides. Each section is to be 5 µm thick.

Biopsy samples taken from bone metastasis and cytology samples are unsuitable for testing and should not be provided. Samples may be collected from primary or metastatic tumour deposits. The mandatory screening tumour biopsy must not be taken from a previously irradiated lesion. The biopsy must not be taken from the lesion(s) selected for inclusion criterion #6 (unless only one measurable lesion exists, in which case the baseline tumour assessment scans are to be done at least 14 days after the screening biopsy).

The second mandatory tumour tissue biopsy will be performed any time between Investigator-assessed, RECIST 1.1-defined progression and before the start of any new anticancer treatment. If a patient discontinues osimertinib before RECIST 1.1-defined progression, the second biopsy will not be performed.

Optional tissue collection

Patients will be asked to consent to provide additional tumour tissue during treatment. The biopsy may be performed between Day 15 and Day 21 of Cycle 1.

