^b Values determined from comprehensive review (internal to AZ) of each compound's PK half-life and determination of the washout period.

^c Estimated value as PK of arsenic trioxide has not been studied.

AZ = AstraZeneca; PK = pharmacokinetics; TdP = Torsades de Pointes.

E 3 Other TdP risk categories

Patients receiving drugs that prolong QT interval or may increase the risk of TdP from other TdP risk categories can be enrolled, notwithstanding other exclusions and restrictions, if these drugs are considered essential for patient management and the patient has been stable on therapy. Close monitoring of ECGs and electrolytes is recommended.

Patients with **congenital long QT syndrome** are excluded from this study.

During study treatment and for a period of 2 weeks after discontinuing study treatment, if it is considered essential for patient management to co-administer drugs known to prolong QTc interval, **regardless of TdP risk category**, close monitoring of ECGs and electrolytes is recommended.

Appendix F Guidelines for Evaluation of Objective Tumour Response Using RECIST 1.1 Criteria (Response Evaluation Criteria in Solid Tumours)

F 1 Introduction

This appendix details the implementation of RECIST 1.1 guidelines ([Eisenhauer et al 2009](#)) for the D5161C00003 study with regards to Investigator assessment of tumour burden including protocol-specific requirements for this study.

F 2 Definition of Measurable, Non-Measurable, Target and Non-Target Lesions

Only patients with measurable disease at baseline should be included in the study. Measurable disease is defined by the presence of at least one measurable lesion which has not been previously irradiated and not chosen for biopsy during the Screening Period.

Measurable:

A lesion, not previously irradiated and not chosen for biopsy during the Screening Period, that can be accurately measured at baseline as ≥ 10 mm in the longest diameter (except lymph nodes which must have short axis ≥ 15 mm) with CT or MRI and which is suitable for accurate repeated measurements. If only one measurable lesion exists, it is acceptable to be used (as a target lesion) as long as it has not been previously irradiated and baseline tumour assessment scans are done at least 14 days after the screening biopsy is performed.

Non-measurable:

- All other lesions, including small lesions (longest diameter < 10 mm or pathological lymph nodes with ≥ 10 to < 15 mm short axis at baseline*)

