Baseline assessments should encompass all areas of known predilection for metastases in the disease under evaluation and should additionally investigate areas that may be involved based on signs and symptoms of individual patients and should be performed no more than 28 days before the start of study treatment (refer to Study Plan and Section 5.1 from the study protocol). Follow-up assessments will be performed every 8 weeks (\pm 7 days) (relative to study enrolment) up to 3.5 years (1277 days) and every 10 weeks (\pm 14 days) from Day 1278 to progression as defined by RECIST 1.1 even if a patient discontinues treatment prior to progression or receives other anticancer treatment. Any other sites at which new disease is suspected should also be adequately imaged at follow-up.

If an unscheduled assessment was performed and the patient has not progressed, every attempt should be made to perform the subsequent assessments at their scheduled visits. This schedule is to be followed in order to minimise any unintentional bias caused by some patients being assessed at a different frequency than other patients.

F 4.2 Target Lesions

F 4.2.1 Documentation of Target Lesions

A maximum of 5 measurable lesions, with a maximum of 2 lesions per organ (including lymph nodes), representative of all lesions involved should be identified as TL at baseline. Target lesions should be selected on the basis of their size (longest diameter for non-nodal lesions or short axis for nodal lesions), but in addition should be those that lend themselves to reproducible repeated measurements. It may be the case that, on occasion, the largest lesion does not lend itself to reproducible measurement in which circumstance the next largest lesion, which can be measured reproducibly, should be selected.

The site and location of each TL should be documented as well as the longest diameter for non-nodal lesions (or short axis for lymph nodes). All measurements should be recorded in millimetres. At baseline the sum of the diameters for all TL will be calculated and reported as the baseline sum of diameters. At follow-up visits the sum of diameters for all TL will be calculated and reported as the follow-up sum of diameters.

Special cases:

- For TL measurable in 2 or 3 dimensions, always report the longest diameter. For pathological lymph nodes measurable in 2 or 3 dimensions, always report the short axis.

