Visit Number	1	2	3	4	5	6	7, 8, 9	10+		Treatment discontinued	28 days ^c	Progression follow-up ^d
Cycles / Day	C1			C2 D1	C3 D1	C4, 5, 6 D1	C7 to 3.5 years D169- 1277	3.5 Years to Disease Progression D1278+				
	D1	D8	D15									
Day	-28 to -1	1	8	15	29	57	85, 113, 141	Every 8 weeks	Every 10 weeks			Every 8 weeks prior to Day 1277/ Every 10 weeks thereafter
Window (Days)		0	±2	±2	±2	±7	±7	±7	±14	±7	+7	± 7/± 14
Physical examination, including weight and eyes ^h	x	x		x	x	x	x	x	x	x		
Height	x											
WHO performance status	x	x		x	x	x	x	x	x	x		once at start of subsequent anticancer treatment
Vital signs	x	x	x	x	x	x	x	x	x	x		

	Screening/ Enrolment ^a	Treatment Period (further treatment cycles as per C7) ^b									Follow-up Period	
Visit Number	1	2	3	4	5	6	7, 8, 9	10+		Treatment discontinued	28 days ^c	Progression follow-up ^d
Cycles / Day		C1							C7 to 3.5 years D169- 1277	3.5 Years to Disease Progression D1278+		
Day	-28 to -1	1	8	15	29	57	85, 113, 141	Every 8 weeks	Every 10 weeks			Every 8 weeks prior to Day 1277/ Every 10 weeks thereafter
Window (Days)		0	±2	±2	±2	±7	±7	±7	±14	±7	+7	± 7/± 14
Clinical chemistry/ Haematology/ Urinalysis ^h	x	x	x	x	x	x	x	x	x	x		
ECG ⁱ	x	x	x	x	x	x	x	x	x	x		
Echocardiogram/ MUGA (for LVEF) ^j	(x)		At least every 16 weeks up to 3.5 years on study drug and then at least every 20 weeks for as long as on study drug							If clinically indicated		
Tumour assessments (RECIST) ^k	x					x	C5D1 and every 8 weeks until Day 1277		Every 10 weeks until progression			x

	Screening/ Enrolment ^a	Treatment Period (further treatment cycles as per C7) ^b									Follow-up Period	
Visit Number	1	2	3	4	5	6	7, 8, 9	10+		Treatment discontinued	28 days ^c	Progression follow-up ^d
Cycles / Day		C1			C2 D1	C3 D1	C4, 5, 6 D1	C7 to 3.5 years D169- 1277	3.5 Years to Disease Progression D1278+			
		D1	D8	D15								
Day	-28 to -1	1	8	15	29	57	85, 113, 141	Every 8 weeks	Every 10 weeks			Every 8 weeks prior to Day 1277/ Every 10 weeks thereafter
Window (Days)		0	±2	±2	±2	±7	±7	±7	±14	±7	+7	± 7/± 14
Dispense study medication		X			X	X	X	X	X			
Dose with osimertinib					Daily dosing							
Concomitant medication and procedures		X	X	X	X	X	X	X	X	X	X	(once) ¹
AEs		X	X	X	X	X	X	X	X	X	X	(once) ¹
First subsequent anticancer treatment ^m											X	X

- ^a Consent must be taken prior to 28-day screening period. Screening period will start with first study-related assessment.

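### Two important-deviation rules in SAP 2.2 contradict the protocol and the SAP itself: the 14-day sole-lesion exemption is inverted, and the scan rule stays 8-weekly after the schedule becomes 10-weekly at Day 1277

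*SAP*

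**What the plan says.** SAP 2.2 lists the categories that count as important protocol deviations, to be listed and discussed in the CSR. Two of them matter here.

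**Biopsy of a RECIST lesion.** This is a deviation "unless only one lesion exists and the RECIST scans are performed within 14 days of screening biopsy". Three other places set the condition for a sole measurable lesion:
- Protocol 5.3.1: "the baseline tumour assessment scans are to be done at least 14 days after the screening biopsy".
- Protocol Appendix F 2: "baseline tumour assessment scans are done at least 14 days after the screening biopsy is performed".
- SAP 3.1.1.1, in the same terms as Appendix F 2.

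**Scan timing.** SAP 2.2 counts as deviations "RECIST 1.1 assessments not done every 8 weeks", with a ±7-day window, anchored on first dose and running to progression. SAP 3.1.1 also describes 8-weekly scans until progression. Elsewhere the schedule changes:
- Protocol 5.1.1 and SAP Table 1 footnote k: 8-weekly scans "from study enrolment until 3.5 years (Day 1277), and then every 10 weeks", with ±14 days.
- Protocol Appendix F 4.1: 10-weekly scans with ±14 days "from Day 1278 to progression as defined by RECIST 1.1".
- SAP Table 1, tumour assessment row: "Every 10 weeks until progression".
- SAP 3.2.2.1: the PFS censoring rule for two missed visits is built on the change from 8-weekly to 10-weekly.

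SAP section 6 states that protocol version 7.0 was used and lists no departure from it.

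**The concern.** Both bullets classify patients against a rule that the protocol does not contain.

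The first runs in the wrong direction. It clears scans taken too soon after the biopsy, which the 14-day requirement does not allow, and flags scans that respected that requirement.

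The second was not updated when the visit interval changed. The SAP's own amendment history shows the change being worked into 3.2.2.1 and 3.3.1 in August and September 2023, so an oversight in 2.2 and 3.1.1 is the likely explanation.

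At stake is the accuracy of the important-deviation listing and summary in the CSR, and of the material put to the pre-lock data review. Compliant long-term patients could be shown as deviators, while breaches of the 14-day rule would go unlisted.

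**Working it through.** **1. Sole-lesion exemption.** Let g = baseline scan date minus biopsy date, in days.
- Protocol 5.3.1, Appendix F 2 and SAP 3.1.1.1 accept g ≥ 14.
- SAP 2.2, for scans after the biopsy, exempts 0 ≤ g ≤ 14.

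| g (days) | Protocol and SAP 3.1.1.1 | SAP 2.2 | Result |
|---|---|---|---|
| 0-13 | not acceptable | exempt | wrongly exempted |
| 14 | acceptable | exempt | agree |
| 15 or more | acceptable | deviation | wrongly flagged |

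Read literally, the SAP wording would also exempt a scan up to 14 days before the biopsy. Long gaps are possible, because inclusion criterion 7 allows tissue obtained "within the 60 days prior to study entry". It is not clear that an archival sample counts as a screening biopsy for this rule. The documents give neither the number of sole-lesion patients nor their gaps.

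**2. Does the SAP itself use the 10-weekly schedule?** SAP 3.2.2.1 states the length of two missed visits, and its figures reproduce:
- from baseline: 2×56 + 7 = 119 days
- 8-weekly period: 2×56 + 7 + 7 = 126 days
- transition: 2×63 + 7 + 14 = 147 days
- 10-weekly period: 2×70 + 14 + 14 = 168 days

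So the censoring rule uses the schedule that SAP 2.2 omits.

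**3. Scan rule measured between scans, after Day 1277.**
- SAP 2.2 accepts 56 ± 7 = 49 to 63 days.
- The protocol permits 70 ± 14 = 56 to 84 days, which is 84 − 56 + 1 = 29 lengths.
- Overlap: 56 to 63 days, 8 lengths.
- Flagged although permitted: 29 − 8 = 21 lengths (64 to 84 days). The nominal 70 days is 7 days beyond the SAP limit.

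**4. Scan rule on a fixed grid from first dose.** The 8-weekly slots fall on day 1 + 56k. The 16 ten-weekly targets in SAP Table 7 are 1303 + 70i, for i = 0 to 15 (D1303 to D2353). The distance to the nearest slot cycles 14, 28, 14, 0 days. Only D1513, D1793, D2073 and D2353 coincide with a slot, so 12 of 16 targets lie outside every ±7-day window. Table 7 defines safety-visit windows, and the count assumes a first-dose anchor, so this is an illustration.

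**5. How many patients could reach this period.** Protocol 8.1 assumes exponential progression times with a 19-month median and 150 patients.
- 1303 / 30.4375 = 42.81 months
- S = exp(−ln 2 × 42.81 / 19) = 0.2098
- 150 × 0.2098 = 31.5, about 31 patients expected to be progression-free at Day 1303

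The binomial standard deviation is √(150 × 0.2098 × 0.7902) ≈ 5, so roughly 22 to 41 is plausible even if the assumed curve is right.

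**The case against.** The strongest reply is that SAP 2.2 offers general categories to be applied as suits the study, and SAP 4.2.3 has the study team define and classify every deviation before lock. A 10-weekly scan that follows protocol version 7.0 is not a protocol deviation, and neither is a sole-lesion scan 15 or more days after biopsy. A sensible reviewer would not list either one. This stands to the extent that misclassification is avoidable rather than automatic. It does not correct the text, and it does little for the opposite error: a scan 0-13 days after biopsy is expressly excused, so nothing prompts a reviewer to look for it.

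It is also fair that the route to sensitivity analyses is weak. SAP 2.2 ties them to deviations that could affect the primary analysis, which is the marker proportion at progression. The documents give no reason why late scan intervals or a short biopsy-to-scan gap would move that proportion.

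A reader might infer more than the documents support in three ways:
- **That efficacy or marker results are compromised.** PAS and FAS membership and PFS censoring do not use these rules.
- **That about 31 patients is a ceiling or a count of wrongly flagged patients.** It is an expected count under an assumed curve. A longer true median would raise it; loss to follow-up, the data cut-off and late adoption of the 10-weekly schedule would lower the number actually exposed.
- **That the 42-day screening limit in SAP 2.2, against 28 days elsewhere, or the first-dose versus enrolment anchor, are further errors of the same kind.** The first may be a deliberate tolerance, since Protocol 3.7.1 lets an extension of screening be discussed. Both are separate queries and form no part of this point.

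**Conclusion.** Both rules are wrong as written, and the contradictions lie in current text. For scans after the biopsy, the sole-lesion exemption matches the protocol only at a gap of exactly 14 days. After Day 1277 the scan rule rejects the nominal 10-week interval and 21 of 29 permitted interval lengths when measured between scans; on a first-dose grid it rejects 12 of 16 illustrative target days. The interval figures assume that the windows apply to the gap between consecutive scans, and the grid figure assumes the SAP 2.2 anchor. The actual number of patients affected cannot be derived. The consequence is limited to the important-deviation listing and summary and the pre-lock review. No PAS, FAS, marker, ORR or PFS result changes. It should be corrected because the rules are wrong and the correction is cheap, not because any estimate is at risk.

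**What to change.** 1. In SAP 2.2, reword the exemption to match SAP 3.1.1.1 and Protocol 5.3.1: only one *measurable* lesion exists (the SAP bullet omits that word), and the baseline scan is at least 14 days after the biopsy.
2. In SAP 2.2, split the scan rule at Day 1277 to match Protocol 5.1.1: 8 weeks ±7 days up to that day, 10 weeks ±14 days after it.
3. Make the same schedule correction in SAP 3.1.1.
4. Have the study team state before lock how late switchers are classed. SAP 3.2.2.1 records that the move to 10-weekly visits varied because protocol version 5.0 was enacted late. Under the corrected rule, measured between scans, a patient still on the 8-weekly schedule passes at 56-63 days but fails at 49-55 days. The rule needs a defined limit, not an open-ended exemption that could hide real deviations.

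The cost is two bullets, one sentence, one classification decision and a re-run of the deviation listing. The important-deviation count may change; no efficacy or marker output needs re-running.
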